[figure not shown]

An Analysis Into the Cause and Preventional Method of Thromboembolic Disease in
Gynecological Surgery

2018.06.01

Study objectives The primary objective of this part is to describe the situations of thromboembolic disease in gynecological surgery like the different symptoms and locations of embolism. The secondary objective of this study is to identify the risk factors of thromboembolic disease using multiple linear regression analysis.

Trial design This is an retrospective cross-sectional observatory trial. After signing of informed consent, the electronic medical data of patients undergoing gynecological surgery but developing embolism unfortunately will be analyzed retrospectively in this study. The symptoms of embolism like dyspnea, chest pain, hemoptysis and syncope during the procedure is spoken by patines and recorded by her doctor in charge. They are also responsible for writing down the location of embolism. All patients have complete blood counts before the operation and on the second or the third post-operative day. The risk factors of it can be identified using the multiple linear regression analysis. An overview of the study design is shown in Figure 1.

Sample size The planned sample size was based on data from a previous study, in which the standard deviation was 5. We assumed an one-tailed α error of 0.05 and a sampling error of 1.0. we propose to enroll 60 participants and allow for a dropout rate of 10% for an effective sample size of 54.

Inclusion criteria

1. Volunteer to participate in the study with informed consent;
2. Females aged 20-80 who are confirmed with some gynecological diseases and are treated with surgery but embolism happens unfortunately.

Exclusion criteria

1. Pregnancy, lactation, postmenopause, or planned pregnancy within two years;
2. Patients with blood diseases prone to thrombosis and those with a history of thrombus were excluded;
3. History of hyperparathyroidism, infectious diseases (tuberculosis, AIDS), autoimmune diseases, or digestive system diseases (malabsorption, crohn disease and dysentery);
4. Other diseases or heavy injuries that will interfere with the results;
5. Simultaneous participation in another clinical study with investigational medicinal product(s) or researcher thinks the subjects are not suitable for this trial.

Outcomes measures

The primary outcome is the percentage of different symptoms of thromboembolic disease(%) The secondary outcomes are the location of embolism according to the results of multiple linear regression analysis.

Withdrawal Subjects must be withdrawn from the study when one of the following criteria occurs:

1. At their own request. At any time during the study and without giving reasons, a subject may decline to participate further. The subject will not suffer any disadvantages as a result;
2. In the investigator's opinion, continuation of the study treatment would be harmful to the subject's health;
3. Obvious non-compliance;
4. Lost to follow-up;
5. Pregnancy;

Safety assessments Safety will be assessed by renal and liver function test, electrolyte, routine blood test. Other indicators are detected during the operation and rehabilitation period. The occurrence of any adverse events in participants will be recorded in the case report forms during each patient visit. We will withdraw patients who have severe adverse events, as it is unsafe for them to continue the trial. Meanwhile, we will give them relevant medical care and follow them up until the reaction has terminated.

Statistical analysis

Multiple linear regression analysis was applied to evaluate the risk factors of embolism related to 14 independent variables including four qualitative variables(hypertension, diabetes mellitus, diagnosis according to the FIGO staging system and the pathological tumor type) and eight quantitative variables (age, BMI, the number of lymph nodes, the interval between biopsy and operation, surgical time, surgical bleeding, postoperative anticoagulant time, preoperative value of Hb, preoperative value of RBC and preoperative value of Hct). All statistical analyses were performed by SPSS 17.0 software package and the level of statistical significance was set at $P<0.05$. All independent variables were incorporated into the model using the method of “Enter”. Data are

presented as mean \pm standard deviation.

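### Every enrolled patient already has an embolism, so the planned regression cannot identify risk factors of embolism

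*Combined protocol and SAP*

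**What the plan says.** **Who is studied.** Trial design: "the electronic medical data of patients undergoing gynecological surgery but developing embolism unfortunately will be analyzed retrospectively in this study". Inclusion criterion 2: "Females aged 20-80 who are confirmed with some gynecological diseases and are treated with surgery but embolism happens unfortunately". The Sample size section describes one group, with 60 enrolled and 54 effective. No section describes surgical patients without embolism or an external rate for comparison.

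**What is claimed.** Study objectives: "The secondary objective of this study is to identify the risk factors of thromboembolic disease using multiple linear regression analysis". Trial design repeats it: "The risk factors of it can be identified using the multiple linear regression analysis". The Statistical analysis section applies the regression to risk factors of embolism, with 14 independent variables all forced into the model.

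**What could be the dependent variable.** The plan does not name one.
- The Outcomes measures section gives location of embolism as the secondary outcome and ties it to the regression.
- Location is written down by the treating doctors: "They are also responsible for writing down the location of embolism".
- The Sample size section relies on "data from a previous study, in which the standard deviation was 5" but does not say which variable this is.

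**The descriptive aim.** "The primary objective of this part is to describe the situations of thromboembolic disease in gynecological surgery". Symptoms and sites are named there as examples. The primary outcome is the percentage of each symptom.

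**The concern.** A risk factor for an event is something more common, or higher, in people who have the event than in comparable people who do not. A study that admits only people with the event never observes the second half of that comparison. The plan's only regression is written for an objective that its own entry criterion rules out.

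What is at stake is the conclusion drawn. If the model is run on location and reported under the heading of risk factors, readers will take differences between embolism sites as causes of embolism. A real risk factor may then look unrelated or even protective.

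**Working it through.** **Inputs from the plan.** 60 enrolled with 10% dropout gives 60 × 0.9 = 54, as stated. Embolism is required for entry. There are 14 independent variables. Whether 54 follows from the stated standard deviation and sampling error is a separate question and has no bearing here.

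**Reading 1: the dependent variable is embolism.** Every patient has y = 1, so the mean is 1 and the total sum of squares is 54 × (1 − 1)² = 0. A least-squares fit with 14 simulated covariates returned slopes of zero, apart from rounding error. Nor do cases alone fix an odds ratio. With exposure among cases assumed to be 50%, the odds ratio is (0.5/0.5) ÷ (p/(1 − p)), where p is exposure among non-cases:

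| p (not collected) | Odds ratio |
|---|---|
| 20% | 4.0 |
| 50% | 1.0 |
| 80% | 0.25 |

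The same case data fit all three, and more cases would not change that.

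**Reading 2: the dependent variable is location.** Assume two mutually exclusive sites with equal baseline risk b. In exposed patients the risks are RR1 × b and RR2 × b. The odds of site 1 against site 2 are therefore RR1/RR2 among exposed cases and 1 among unexposed cases. The site odds ratio among cases is RR1/RR2. The overall relative risk of embolism is (RR1 + RR2)/2.

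| RR1, RR2 | Overall relative risk | Site odds ratio among cases |
|---|---|---|
| 2, 2 | 2.0 | 2/2 = 1.0 |
| 2, 4 | 3.0 | 2/4 = 0.5 |
| 1.5, 0.5 | 1.0 | 1.5/0.5 = 3.0 |

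In row 1 a true risk factor is invisible. In row 2 a true risk factor has an odds ratio below 1. In row 3 the association with location is real, but there is no effect on overall risk of embolism. Location is also a category, which linear regression does not suit.

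**Reading 3: some continuous quantity.** It is still measured only in patients with embolism, so the comparison is again between cases.

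**How much a correct location model could show.** Assumptions: 54 cases, two location groups, one binary exposure with prevalence p0 of 10% to 50% in the reference group, 80% power, two-sided 0.05, no adjustment.

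- Exposure in the other group: p1 = OR × p0/(1 − p0 + OR × p0).
- Power: Φ[(|p1 − p0| − 1.96 × SE0)/SE1], with SE0 from the pooled and SE1 from the unpooled variance.
- Example, 27/27 split, p0 = 30%, OR = 4.8: p1 = 1.44/2.14 = 0.673, SE0 = 0.136, SE1 = 0.126. Then (0.373 − 0.267)/0.126 = 0.84, which is 80% power.
- Detectable odds ratio at an assumed 27/27 split, for p0 = 10, 20, 30, 40, 50%: 6.76, 5.14, 4.80, 4.96, 5.64. The range is about 4.8 to 6.8.
- At an assumed 11/43 split the same formula gives 8.52, 6.89, 6.93, 8.04, 11.54. Putting SE1 in place of SE0 gives 10.57, 7.11, 6.15, 5.94, 6.22. The answer is roughly 6 to 12 and depends on the approximation.
- Adjustment raises these values. If other covariates explain 20% of the exposure's variance (assumed), the effective number falls to 54 × 0.8 = 43.2.

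**The case against.** **A comparison group may exist elsewhere.** The primary objective speaks of one part of the study, which hints at a wider project, and Figure 1 is not available to this review. Neither is held against the plan. But the written entry criterion excludes patients without embolism, and no section brings them in.

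**Risk factors may be loose wording for factors related to location.** This is the most charitable reading, and the secondary outcome supports it. A case-only analysis of location is a legitimate question. It is still not the stated objective, and the remedy is then to say so and choose a suitable model.

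**This is a secondary objective in a small descriptive study.** That stands, and it limits the point to the risk-factor claim and the regression behind it. A reader might infer that the whole study fails. The documents do not support that: symptom percentages among patients with embolism need no comparison group.

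**The figures rest on assumptions.** Also true. The sites, relative risks, prevalences and splits are not in the plan. They illustrate size and direction, and the main point depends on none of them.

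**Conclusion.** The point holds. As written, the regression either has a constant outcome or yields contrasts between cases that would be mislabelled as risk factors of embolism. This follows from the entry criterion alone and is the same at any sample size. It should be corrected before analysis.

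Three stronger inferences are not supported.
- One cannot say that the regression will fail to run, because the plan does not state that embolism is the dependent variable.
- One cannot say that every location finding would be false. A site odds ratio of 3.0 from relative risks of 1.5 and 0.5 is a true association with location. Only the risk-factor label is wrong.
- One cannot say that controls must be added. The plan can be made coherent without them.

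The detectable odds ratios (about 4.8 to 6.8, or roughly 6 to 12) are unadjusted, rest on the stated assumptions, and are rough at the uneven split.

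**What to change.** Choose one. Both change text and analysis only.

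**(A) Keep a regression, on location.**
- Reword the secondary objective, the Trial design sentence, the secondary-outcome sentence and the Statistical analysis section to *factors associated with the location of embolism among patients with embolism*, labelled exploratory.
- Name location as the dependent variable, with mutually exclusive categories and a coding rule for patients with more than one location.
- Replace linear regression with logistic regression for two groups, or multinomial regression only if numbers allow.
- State the detectable odds ratios above, with their assumptions, as a limitation.

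**(B) Drop the regression and the risk-factor claim.** Report location descriptively with 95% confidence intervals, and delete the clause in the secondary-outcome sentence that ties location to the regression. For scale, Wilson intervals would be 37% to 63% for 27/54 and 12% to 33% for 11/54.

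**Cost.** Either way, the study gives up its claim to identify risk factors. Doctors are already charged with recording location, so no new variable is needed. The plan does not say that the record is complete or coded in exclusive categories, so (A) adds a coding step and remains a weak comparison.

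Adding embolism-free surgical patients is optional and not part of this fix. It is not cheap: 54 further records at 1:1 or 108 at 1:2, consent or a waiver for those patients, and an ethics amendment.

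### The sample-size figures do not agree: SD 5 and a sampling error of 1.0 need 68 (one-tailed 0.05) or 97 (two-sided) evaluable patients, and the planned 54 give a margin of 1.12 or 1.33

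*Combined protocol and SAP*

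**What the plan says.** All planning inputs stand in the Sample size paragraph of the combined protocol and SAP. On the SD: "The planned sample size was based on data from a previous study, in which the standard deviation was 5". On the error level and precision: "We assumed an one-tailed α error of 0.05 and a sampling error of 1.0". On the numbers: "we propose to enroll 60 participants and allow for a dropout rate of 10% for an effective sample size of 54". The paragraph does not name the variable to which the SD and the sampling error belong, gives no units, and states no power.

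The Statistical analysis section describes the regression: "Multiple linear regression analysis was applied to evaluate the risk factors of embolism related to 14 independent variables". On entry it says "All independent variables were incorporated into the model using the method of “Enter", and on the threshold "the level of statistical significance was set at $P<0.05". It gives no side for the tests and no expected direction for any variable. The one-tailed level in Sample size is the only mention of sidedness in the document, and neither section refers to the other's error level.

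**The concern.** A sample-size statement should let a reader get from the inputs to the number of patients. This one gives an SD, an error level and a precision, which is all that a precision calculation needs, yet the result does not look like 54 or 60. If so, the document promises a tighter estimate than the study can give, and anyone who relies on the margin of 1.0 is misled.

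The choice of side makes this worse. A sampling error is usually read as a margin on both sides of an estimate. On that reading, a one-tailed 0.05 corresponds to a 90% interval and not the customary 95% one. It is also an odd companion to an open search for risk factors, where no sign is fixed beforehand and where a factor with several categories, as tumour type may be, has no single direction to test.

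**Working it through.** **Inputs (all from Sample size).** SD = 5; sampling error E = 1.0; α = 0.05 one-tailed; 60 enrolled; 10% dropout; 54 evaluable.

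**Step 1: the dropout step.** 60 × (1 − 0.10) = 54. This reproduces.

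**Step 2: evaluable patients needed for the stated margin.** n = (z × SD / E)².

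| Reading of α = 0.05 | z | n | Enrolled, n / 0.90 |
|---|---|---|---|
| One-tailed | 1.645 | (1.645 × 5 / 1.0)² = 67.6, so 68 | 76 |
| Two-sided | 1.960 | (1.960 × 5 / 1.0)² = 96.0 (96.04 before rounding up), so 97 | 108 |

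With t quantiles in place of z, the evaluable numbers are 70 and 99. Neither 54 nor 60 appears.

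**Step 3: could it be a test and not a precision statement?** No power is stated, so 80% is an assumption. A one-sample, one-tailed test to detect a difference of 1.0 needs ((1.645 + 0.842) × 5 / 1.0)² = 154.6, so 155. The two-sided, 90%-power and two-group variants need more. This reading moves further from 54.

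**Step 4: margin that the planned size gives.** Margin = z × SD / √n, with √54 = 7.348 and √60 = 7.746.

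| n | One-tailed 0.05 | Two-sided 0.05 |
|---|---|---|
| 54 | 1.645 × 5 / 7.348 = 1.12 | 1.960 × 5 / 7.348 = 1.33 |
| 60 | 1.06 | 1.27 |

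Even with no dropout, the margin does not reach 1.0.

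**Step 5: what would make the stated figures agree.** With n = 54 and E = 1.0, z = 1.0 × 7.348 / 5 = 1.470, which is α = 0.071 one-tailed or 0.142 two-sided. Alternatively, at the stated E the SD would have to be 7.348 / 1.645 = 4.47 (one-tailed) or 7.348 / 1.960 = 3.75 (two-sided). The paragraph gives none of these values.

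**Step 6: the side of the regression tests.** If each of the 14 variables enters as one coefficient (an assumption, since category counts are not given), the residual degrees of freedom are 54 − 14 − 1 = 39. The cut-off for |t| is then 1.685 at one-tailed 0.05 and 2.023 at two-sided 0.05. With 12 to 20 terms the ranges are 1.683–1.692 and 2.020–2.035. These figures show how far apart the two levels lie. They do not show that the plan uses both.

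**The case against.** The strongest defence is that the one-tailed 0.05 is a planning input and nothing more. A reader might infer that the plan holds two rival standards for the regression, so that a coefficient with a two-sided P between 0.05 and 0.10 is declared a risk factor or not according to which sentence is applied, with a real error rate of 10% per variable. The documents do not support that. The only rule for declaring a risk factor is P below 0.05 from SPSS, whose coefficient P values are two-sided by default (general knowledge of the software, not a statement in the plan). A one-tailed verdict would need the analyst to halve those values, and nothing in the plan asks for it. Nor can one say how often results would fall between the two cut-offs, because the plan gives no effect size. This part of the defence stands.

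It is also fair that one-sided confidence bounds are legitimate, so one-tailed 0.05 is not wrong in itself. But the arithmetic does not depend on that: 54 falls short of 68 on the one-tailed reading too.

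A third objection is that writing in 1.33 fits the precision to a number already chosen, for a quantity that is not named, while the primary outcome in Outcomes measures is a percentage. That is true. The restatement makes the figure honest; it does not justify the choice of 60.

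**Conclusion.** The point holds for the planning statement. The stated SD, error level, margin and number of patients cannot all be right together. The planned 54 is 14 short of the 68 needed at one-tailed 0.05 and 43 short of the 97 needed at two-sided 0.05. Put the other way, the margin is 12% or 33% wider than stated.

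This rests on reading the sampling error as the half-width of an interval for a mean and on the normal quantile; t quantiles make the gap slightly larger. The units of the margin are unknown until the variable is named.

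The missing side in Statistical analysis is a matter of clarity only. It touches the secondary objective, since the primary outcome is a descriptive percentage for which no test is planned. Settling the side would not by itself repair the sample size, because neither side reproduces it.

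**What to change.** In Sample size, replace "We assumed an one-tailed α error of 0.05 and a sampling error of 1.0" with: 'We assume two-sided 95% confidence and a margin of 1.33 (SD 5, 54 evaluable).' Add the name and units of the variable to which the SD refers. Keep enrolment at 60.

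In Statistical analysis, as a minor clarification, add: 'Regression tests are two-sided at 0.05.'

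The cost is a few words and no extra patients. The stated margin becomes less favourable, 1.33 in place of 1.0. If the sponsor needs 1.0, wording will not supply it: that takes 76 enrolled at one-tailed 0.05 or 108 at two-sided 0.05, allowing for 10% dropout.

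### The sample-size argument is built for a mean, gives no precision for the percentage primary outcome, and does not lead to 54 from its printed inputs

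*Combined protocol and SAP*

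**What the plan says.** All passages are in the combined protocol and SAP.

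- **Sample size**, inputs: "The planned sample size was based on data from a previous study, in which the standard deviation was 5", followed by "We assumed an one-tailed α error of 0.05 and a sampling error of 1.0". The section does not name the variable measured, its unit, the formula, or a power.
- **Sample size**, result: "we propose to enroll 60 participants and allow for a dropout rate of 10% for an effective sample size of 54".
- **Outcomes measures**: "The primary outcome is the percentage of different symptoms of thromboembolic disease", with the unit given as %.
- **Trial design** names several symptoms: "The symptoms of embolism like dyspnea, chest pain, hemoptysis and syncope". It does not say whether a patient can count under more than one, or whether the percentage is taken over patients or over reported symptoms.
- **Statistical analysis** covers the multiple linear regression and says that data are "presented as mean \pm standard deviation". It gives no interval for a percentage.

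**The concern.** There are two separate problems.

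First, an SD with an absolute error is the input for a mean, whereas the primary outcome is a percentage. In a single-group descriptive study, the precision of the primary estimate is the main thing a sample-size paragraph can justify, and here it is missing. A reader who sees "a sampling error of 1.0" next to an outcome in % could also suppose that the symptom percentages will be known to about one point.

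Second, the number offered in its place cannot be checked. The formula, variable, unit and unrounded inputs are absent, and the usual formula applied to the printed values does not give 54.

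**Working it through.** **The plan's own dropout step.** 60 × 0.9 = 54, and 54 / 0.9 = 60. This reproduces.

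**From the inputs to N.** Inputs from Sample size: SD = 5, error d = 1.0, one-tailed α = 0.05, so z = 1.6449. The plan states no formula, so I assume the usual one for the precision of a mean:

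n = (z × SD / d)² = (1.6449 × 5 / 1.0)² = 67.64, so 68 evaluable; 68 / 0.9 = 75.6, so 76 enrolled.

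Other conventions do not recover 54, or 60 read as the number before dropout:

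- two-sided z: 97 evaluable, 108 enrolled
- t-based iteration: 70 (one-sided), 99 (two-sided)
- one-sample test at 80% or 90% power (assumed, as no power is stated): 155 or 215 one-sided, 197 or 263 two-sided
- comparison of two means: 310 or more per arm
- finite-population correction from 68 down to 54: needs a population of about 258, which is not stated

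**Could rounding explain it?** Let SD lie between 4.5 and 5.5, and d between 0.95 and 1.05.

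- Smallest n: (1.6449 × 4.5 / 1.05)² = 49.69, so 50.
- Largest n: (1.6449 × 5.5 / 0.95)² = 90.68, so 91.
- n ≤ 54 requires SD/d ≤ √54 / 1.6449 = 4.468. Within the rounding limits this means SD no larger than 4.69 (at d = 1.05) and d no smaller than 1.007 (at SD = 4.5). For example, SD 4.6 with d 1.03 gives 53.96.

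Rounding is therefore a possible explanation, but both inputs must have been rounded in the helpful direction.

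**What the stated sizes give on the mean scale, with SD exactly 5.** d = 1.6449 × 5 / √54 = 1.119 at 54 evaluable, and 1.6449 × 5 / √60 = 1.062 at 60.

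**Could the inputs be percentage points?** A yes/no symptom with frequency p has SD √(p(1 − p)). An SD of 5 points corresponds to p of about 0.25% (or 99.75%), which is not a useful planning value, and the formula would still return 68. At p = 50%, an error of 1 point needs 1.6449² × 0.25 / 0.01² = 6,764 patients one-sided, or 9,604 two-sided.

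**Precision for the primary outcome.** I assume that the denominator is all evaluable patients. The two-sided 95% Wilson interval, with p = x/n and z = 1.96, has half-width z√(p(1 − p)/n + z²/(4n²)) / (1 + z²/n). At n = 54:

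| Patients with symptom | 95% Wilson interval | Half of total width (points) |
|---|---|---|
| 27/54 | 37.1% to 62.9% | 12.9 (maximum) |
| 11/54 | 11.8% to 32.9% | 10.6 |
| 5/54 | 4.0% to 19.9% | 7.9 |
| 0/54 | 0% to 6.6% | 3.3 |

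The maximum half-width is 12.3 points with 60 evaluable and 14.0 with 45. Exact intervals at n = 54 have a half-width of at most 13.9 points (27/54: 36.1% to 63.9%). The symptom counts are illustrations; the documents give no expected frequencies.

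**The case against.** The strongest reply concerns the arithmetic. The plan prints no formula, so 68 and 76 rest on one supplied from outside, and the rounding range of about 50 to 91 contains 54. That shows a number that cannot be verified, not a proven miscalculation, and the one arithmetic step the plan does print is right. This stands, and the claim is limited to it: 54 does not follow from the inputs as printed.

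It can also be said that little turns on 54 versus 68. The study is retrospective and single-group, the primary outcome carries no confirmatory test, and 1.12 against 1.0 is a modest difference. This stands too, and it is why a wording change is enough.

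Finally, the mean ± SD rule is probably meant for the quantitative variables, since the outcome definition already gives a percentage as the summary. That is a fair reading, but the plan does not say so, and it still supplies neither an interval nor a denominator.

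None of this touches the first problem. If the SD belongs to some secondary variable, or if unrounded inputs do produce 54, the primary outcome still has no stated precision. The sample-size paragraph reads as complete and shows no sign of redaction.

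**Conclusion.** The concern holds. That the justification does not address the primary outcome follows from the text alone, without any assumed formula. With 54 evaluable patients, a symptom percentage would have a two-sided 95% Wilson half-width of up to about 13 points, provided the denominator is all evaluable patients.

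That 54 does not reproduce is the lesser part and depends on the assumed formula for a mean. On that formula the printed inputs require 68 evaluable, 14 more than planned, or equivalently the error at 54 is 1.12 if the SD is exactly 5. Unrounded inputs with a ratio of 4.47 or less would remove this discrepancy, but the plan does not give them.

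**What to change.** Keep 60 enrolled and 54 evaluable, and replace the Sample size justification with a statement of expected precision. Suggested text, with the denominator and the multiple-symptom clause to be confirmed by the sponsor because the plan states neither:

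> The denominator is all evaluable patients, and a patient may have more than one symptom. With 54 evaluable patients, the two-sided 95% Wilson interval for the percentage of patients with a given symptom has a half-width of at most about 13 percentage points (27/54: 37.1% to 62.9%; 11/54: 11.8% to 32.9%; 5/54: 4.0% to 19.9%; 0/54: 0% to 6.6%).

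In Statistical analysis add:

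> Each symptom is reported as n/N (%) with a two-sided 95% Wilson interval, where N is all evaluable patients; mean ± SD is used for quantitative variables only.

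If the sponsor means the share among all reported symptoms, the plan should say so; these intervals then do not apply. Exact intervals would serve equally well, with the maximum restated as 13.9 points. If the mean-based calculation is kept alongside, give its formula, variable, unit and unrounded SD and error, or restate the error as 1.12 at n = 54 if the SD is 5.

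This text discloses what 54 patients deliver. It does not show that about 13 points is sufficient, which the sponsor should judge and state.

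The cost is wording in two sections, with no change to enrolment. The downside is presentational: the plan would openly state a precision of about 13 points for its primary outcome, and 1.12 in place of 1.0 if the mean-based figure stays with an SD of 5.

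### Linear regression is planned for location of embolism, an unordered category: with three or more sites, slopes, signs and P<0.05 verdicts depend on arbitrary site codes

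*Combined protocol and SAP*

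**What the plan says.** Under Study objectives: "The secondary objective of this study is to identify the risk factors of thromboembolic disease using multiple linear regression analysis". Trial design repeats this ("The risk factors of it can be identified using the multiple linear regression analysis") and says of the treating doctors: "They are also responsible for writing down the location of embolism". Outcomes measures then links location to the model: "The secondary outcomes are the location of embolism according to the results of multiple linear regression analysis".

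The Statistical analysis section specifies one model only: "Multiple linear regression analysis was applied to evaluate the risk factors of embolism related to 14 independent variables". All predictors are forced in together by the Enter method, and significance is set at P<0.05.

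The second inclusion criterion restricts the sample to women who "are treated with surgery but embolism happens unfortunately".

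The plan gives no list of sites, ordering, numeric code or per-site indicator, and no logistic or multinomial model. It does not say how a patient with more than one site is counted.

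**The concern.** Linear regression needs a dependent variable whose numerical differences mean something. The plan offers two candidates, and neither qualifies.

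- **Location** is a nominal category. With three or more sites, each must be assigned a number, and nothing in the plan or in the nature of the variable says which site gets which.
- **Embolism** is present in every enrolled patient, so it has no variation. No regression, linear or logistic, can identify risk factors for embolism in this sample.

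This regression is the only inferential analysis in the plan, and the whole secondary objective rests on it. Two analysts with the same data and equally defensible codes could report different significant factors, in some patterns with opposite signs.

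**Working it through.** **Inputs from the protocol.** Effective sample size 54 (Sample size); 14 predictors, all entered, P<0.05 (Statistical analysis); location as the outcome tied to the regression (Outcomes measures). The plan states no figure for this analysis, so there is none to reproduce.

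**Assumptions.** Number of sites (three unless stated), site shares, effect sizes, independent normal predictors and two-sided coefficient tests.

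**Step 1: algebra, one predictor.** Let sites A, B and C have codes c_g, n_g patients and predictor means x̄_g. The least-squares slope is

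b = Σ c_g n_g (x̄_g − x̄) / Sxx.

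With 18 patients per site this reduces to

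- codes A,B,C = 1,2,3: b = 18(x̄_C − x̄_A)/Sxx
- codes 1,3,2: b = 18(x̄_B − x̄_A)/Sxx
- codes 2,1,3: b = 18(x̄_C − x̄_B)/Sxx

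Each coding thus tests a different contrast between two sites. The remaining three orderings are mirror images, which reverse the sign and leave the p-value unchanged.

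**Step 2: constructed example.** Take mean ages 50, 60 and 50 at A, B and C, with within-site SD about 8. The overall mean is 53.33. The between-site sum of squares is 18 × (3.33² + 6.67² + 3.33²) = 1,200 and the within-site sum is 3,221, so Sxx = 4,421.

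| Codes A,B,C | Numerator | Slope per 10 years | P |
|---|---|---|---|
| 1,2,3 | 18 × (50 − 50) = 0 | 0.00 | 1.00 |
| 1,3,2 | 18 × (60 − 50) = 180 | +0.41 | 0.0006 |
| 2,1,3 | 18 × (50 − 60) = −180 | −0.41 | 0.0006 |

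A one-way ANOVA of age by site, which ignores the codes, gives P = 0.0003 under any labelling.

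**Step 3: simulation of the planned model.** n = 54, three equally common sites, 14 predictors entered together, 4,000 datasets per scenario. Percentages are for one chosen predictor.

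| True effect of that predictor | Significant under 1,2,3 / 1,3,2 / 2,1,3 | Verdict differs between codings |
|---|---|---|
| Odds of B × 2.7 per SD | 4% / 63% / 62% | 78% |
| Odds of B × 2.0 per SD | – | 54% |
| Odds of B × 1.5 per SD | – | 30% |
| Graded A to C, odds ratio 2.7 for C versus A | 66%, 21% or 20% by coding | 69% |
| None | 5–6% each | – (13% reach P<0.05 under at least one coding) |

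In the first row the mean slopes are 0.00, +0.29 and −0.29. Repeat runs gave disagreement of 78–79%, 54–56%, 29–30% and 69–70% for the four non-null rows. At an odds ratio of 2.7 for B, it was 75% with site shares of about 50/30/20 and 80% with four sites.

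Significant slopes of opposite sign occurred in 46% of datasets at odds ratio 2.7, about 21% at 2.0, 7% at 1.5, and essentially none in the graded pattern.

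**Step 4: two sites.** Any pair of distinct codes gives identical p-values; swapping them only reverses the sign.

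**Step 5: can the same 14 predictors simply move to a categorical model?** No. A three-site multinomial model then has 2 × (14 + 1) = 30 parameters for 54 patients. Its unpenalised likelihood-ratio test at 0.05 rejects a true null in 17% of datasets; unpenalised binary logistic regression rejects in 11%. Firth-penalised binary or multinomial models with 2–3 predictors reject in 5–6%.

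**The case against.** The strongest reply is that the plan does not clearly make location the dependent variable. One awkward sentence links the two. The objective, the design text and the statistical section all name risk factors for embolism, and the statistical section never mentions location. The sample-size inputs (SD 5, sampling error 1.0) and the promise of means with standard deviations fit a numeric variable better. It is fair to say that the dependent variable is not properly defined. That does not rescue the analysis: no numeric outcome is named, location is the only outcome linked to the regression, and embolism does not vary. Of the two defects, the cases-only sample is the more basic, since it needs no assumption about the number of sites.

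Second, coding dependence of the p-value needs three or more sites. The objectives refer to locations in the plural without a count. This condition stands.

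Third, opposite significant signs are common only when a strong effect is confined to one site. This also stands; disagreement about significance, by contrast, appeared in every non-null pattern examined.

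Fourth, penalised modelling with few predictors is one remedy among several, and description alone would suffice. That is accepted, and the model below is optional.

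**Conclusion.** The concern holds and must be fixed for the secondary objective. For three or more unordered sites, dependence on the coding is algebraic. Its size here is illustrative: under the assumptions above, the verdict for a predictor with a real effect changed with the coding in 30% to 78% of datasets.

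The fault is that the slope has no meaning. It is not inflated type I error: any single coding fixed in advance rejects a true null at about 5%. With exactly two sites the p-values are free of the coding, but the stated aim of finding risk factors for embolism still fails, because all patients have it. The primary outcome, symptom percentages, is untouched.

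**What to change.** 1. Remove multiple linear regression from the objective, design, outcome and analysis sections.
2. List the site categories before analysis and state how a patient with more than one site is counted.
3. Report location as n/N (%) per site with a 95% confidence interval; for example 18/54 = 33%, Wilson interval 22% to 47%. This also serves the primary objective, which is to "describe the situations of thromboembolic disease in gynecological surgery like the different symptoms and locations of embolism".
4. Reword the secondary objective as factors associated with location among patients with embolism, and make no claim about risk factors for embolism itself.
5. If a model is kept, use Firth-penalised binary logistic regression for a two-way split fixed in advance, or penalised multinomial logistic regression for three or more sites. Enter 2–3 pre-specified predictors and report odds ratios with 95% confidence intervals.

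**Cost.** Wording only, with no new data. The conclusion is narrower, fewer predictors are examined, and the penalised models need a free add-on or other software. Power is limited (simulated, equally common sites, effect per SD, 2 / 3 predictors):

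| Odds ratio | Firth multinomial | Firth binary |
|---|---|---|
| 2.7 | 82% / 74% | about 87% |
| 2.0 | 48% / 47% | 67% / 62% |
| 1.5 | 21% / 17% | 31% / 28% |

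Rarer sites would lower these further, so description alone is a reasonable choice.
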